Detailed instructions are included for each section. All instructions must be removed, and all sections completed. "Not Applicable" is an acceptable response if the section does not apply to the research.

1. STUDY TITLE

Prospective single-center study comparing Thulium fiber laser to pulsed Thulium:YAG laser in the ureteroscopic treatment of nephrolithiasis

3. STUDY RATIONALE

To our knowledge no large-scale study has examined the outcomes of p-Tm:YAG compared to TFL for the treatment of kidney stones which warrants an investigation giving the promising results previously reported.

4. SPECIFIC AIMS/HYPOTHESES

Our primary objective is to assess stone dusting ablation efficiency (Joules/stone volume ablated) between both laser systems *in vivo* for ureteroscopic stone treatment (Ventimiglia et al., 2021, 2023; Corrales and Traxer, 2022). Secondary objectives include assessing stone dusting ablation speed (stone volume ablated/lasing time), stone-related clinical outcomes, effect of hard stones (>1000HU) on ablation efficiency, and safety/complication profile of both laser systems.

We hypothesize that dusting ablation efficiency and speed of the p-Tm:YAG laser will be non-inferior to TFL for the treatment of renal stones totaling 7-20 mm in diameter with similar clinical and safety/complication outcomes.

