Laser settings will be adjusted at the surgeons' discretion but begin at 0.3 J and 10 Hz (long pulse mode for Thulio and short pulse for TFL). (Petzold et al., 2021a) At the surgeon discretion the joules and/or frequencies can be increased by smallest increments available. If possible, a stone fragment will be removed and sent for stone analysis. An additional fragment may be sent for culture at the discretion of the surgeon. Adequacy of dusting will be defined as stone fragments smaller than the laser fiber diameter. A ureteral stent will be placed at the conclusion of the surgery. A string will be left on the stent at the discretion of the surgeon. Post-operative medical therapy will be an alpha receptor blocker to induce ureteral relaxation if not contraindicated for allergy, cataracts, or history of adverse reaction. Additionally, standard postoperative pain medications will be prescribed at the discretion of the treating surgeon.

The stent will be maintained for 2 to 21 days after surgery. Low-dose CT abdomen/pelvis will be performed at 6 weeks postoperatively to assess for stone-free rate, development or persistence of hydronephrosis/obstruction, and need for ancillary procedures. Telephone calls at 2, 4, and 6 weeks will be placed by the CRC to determine any unreported AEs. First clinic follow-up after stent removal will be performed at 8 weeks after stent removal. Telephone call at 2, 4 and 6 weeks will be made by CRC to determine any unreported AE's.

Lasing time (s), laser energy expended (J), and estimated % of the case completed with dusting will be recorded at the conclusion of the case from the laser data log.

All study procedures are standard of care except for the randomization aspect, which will randomly assign a patient to one of two laser groups, and data collection.

Demographic fields that will be obtained preoperatively include age, gender, ASA (American Society of Anesthesiologists) score (for comorbidity assessment), height, weight, body mass index (BMI), and primary or recurrent stone, prior stone composition(s). Disease fields that will be obtained include stone volume (calculated with maximal axial and coronal dimensions), average stone Hounsfield units, degree of hydronephrosis (mild/moderate/severe), and prior ureteral stenting or nephrostomy tube placement.

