| | (Azilgareeva et al., 2022) | 25 | 508.9 (293.2-628.3) | 1124.0 ± 329.0 | 15.0 (11.2-18.3) | 0.6 (0.5-0.9) | 30.8 (22.8-41.2) |

The electronic data will be stored in the REDCap (Research Electronic Data Capture) application (16,17). REDCap is a stand-alone system with no interaction or connectivity to other systems, and the database is located behind the UCSD firewall. Users must have a UCSD provided ID/password to connect to REDCap and their ID must be specifically

authorized in order to access an individual study's data. All changes to the data, and each "record viewed" is logged back to the individual ID with a timestamp. When the case report forms are configured, each field has an attribute that can be set to flag it as an "identifier". This "identifier" is used by REDCap to control certain actions related to the field. REDCap also has several built-in functions to control the exporting of identifying information. Individual users are each granted specific export rights, including – None, De-Identified, and Full. Additional export de-identification options include removing identifiers and dates, hashing IDs and date shifting.

Demographic data, pre-operative, and post-operative data will be summarized using mean, median and quartiles (continuous variables) and frequency and percent (categorical variable).

Intention-to-treat analysis will be performed. Non-inferiority analysis will be conducted for the primary endpoints, with a pre-specified non-inferiority margin of 20%.

Secondary endpoints will be compared using appropriate statistical tests (e.g., t-test, chi-square test). All analyses will be performed using a statistical software package (e.g., SPSS).

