8. RECRUITMENT

Ureteroscopic treatment of renal calculi is the standard of care treatment approach, and thus no treatments will be performed that are not considered standard of care.

Patients will be identified based on operating room schedule, clinic visits or hospital admission. They will be approached in person by study personnel.

Using block randomization, participants will be randomized in a 1:1 ratio to receive either p-Tm:YAG or TFL treatment. Surgeons will be blinded to the assigned laser treatment until in the operating room.

Project subjects will be chosen from the pool of patients presenting in a UCSD Urology clinic with kidney stone disease who have chosen to undergo flexible ureteroscopy with holmium laser lithotripsy. Females of childbearing age are given a pregnancy test prior to the procedure. No person shall be excluded from being offered the trial except those based on the above inclusion/exclusion criteria. Vulnerable groups such as pregnant women, fetuses; neonates; prisoners; children; groups with known cognitive impairment; or institutionalized individuals will not be involved in this project. This project has neither direct benefit to individual participants nor monetary compensation, and as such is less likely to lead to coercion of patient populations.

This project will be requesting a partial waiver of HIPAA authorization to be granted. Identifiers will be protected from improper use by having access restricted to project personnel which is limited to the PI and project coordinator. Identifiers will be destroyed 4 years after the project initiation or 2 years after data collection is complete. Project recruitment could not be possible without access to medical chart information which includes PHI. This access to PHI poses minimal risk as it is not used for reasons other than identifying potential participants. No PHI will be used as part of data collection for the project except name on the Informed Consent Form.

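### The hard-stone objective rests on a cut at 1000 HU although density is recorded as a continuous value; analyse HU as continuous, and name it as a covariate in the primary comparison

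*Protocol*

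**What the plan says.** Section 4 defines the primary outcome as energy per volume: "Our primary objective is to assess stone dusting ablation efficiency (Joules/stone volume ablated) between both laser systems". Among the secondary objectives it names the "effect of hard stones (>1000HU) on ablation efficiency". No other sentence gives stone density a role in the analysis.

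Section 6 lists among the baseline disease fields "stone volume (calculated with maximal axial and coronal dimensions), average stone Hounsfield units". Both are measured values, not categories.

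On analysis, section 6 states "Non-inferiority analysis will be conducted for the primary endpoints", by intention to treat and with a 20% margin. It names no test, model or covariate for that comparison. For the rest it says "Secondary endpoints will be compared using appropriate statistical tests (e.g., t-test, chi-square test"), which are examples.

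Section 8 states "Using block randomization, participants will be randomized in a 1:1 ratio" and mentions no stratification factor.

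**The concern.** By making hard stones an objective, the protocol treats density as something that may change J/mm³, which is its primary outcome. It then expresses density as two classes. Stones of 990 and 1010 HU fall in different classes, while stones of 1010 and 1500 HU are treated as alike. If the effect of density is gradual, this weakens the objective for no saving, because the continuous value is already in the database.

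The same value could also sharpen the primary comparison if it predicts J/mm³. Precision is scarce there: the planning SD is 5.2 J/mm³ around a mean of 6.2, and the margin is 1.2.

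**Working it through.** **1. Where the cut falls.** The central densities in the TFL rows of Table 1 (section 6) are 900, 900, 950, 985, 986, 990, 1020, 1100 and 1170 HU. Five bracketed spreads are 726-1203, 625-1275, 750-1350, 636-1300 and 725-1125, and each contains 1000. A cut at 1000 is therefore near the middle of these cohorts.

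**2. What a cut keeps.** For a normal predictor with a linear effect, cut at c standard deviations from its mean, the share of information kept is the squared correlation between the predictor and its class:

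φ(c)² / {Φ(c)[1 − Φ(c)]}

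- Cut at the median (c = 0): (1/2π) / (1/4) = 2/π = 0.637. About 36% is lost, like setting aside about 36 of 100 patients for this question.
- Row centred at 900 (625-1275), spread read as an interquartile range (assumption): SD = 650/1.349 = 482, c = (1000 − 900)/482 = 0.21, share kept 0.63.
- Row centred at 1170 (636-1300), same reading: SD = 664/1.349 = 492, c = (1000 − 1170)/492 = −0.35, share kept 0.61.

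For a normal predictor the median is the cut that loses least, so the result is not sensitive to where in this range the trial's median lies. It is sensitive to linearity: if the effect were a true step at 1000 HU, the cut would lose nothing.

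**3. What continuous HU could add to the primary comparison.** If HU explains a share R² of the variance, the residual SD is 5.2·√(1 − R²) and the gain in effective sample size is 1/(1 − R²). The protocol gives no R², so 0.1 to 0.4 is an assumed range. With 50 per arm the 95% half-width is 1.984 × SD × √(2/50):

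| R² | 1/(1 − R²) | SD | Half-width (J/mm³) |
|---|---|---|---|
| 0 | 1.00 | 5.20 | 2.06 |
| 0.1 | 1.11 | 4.93 | 1.96 |
| 0.4 | 1.67 | 4.03 | 1.60 |

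On a log scale, the planning interquartile range of 3 to 9.9 gives a log SD of ln(9.9/3)/1.349 = 0.885. The interval factor exp(1.96 × 0.885 × √[(1 − R²) × 2/50]) is then 1.41 at R² = 0, 1.39 at 0.1 and 1.31 at 0.4. This is illustrative only. The planning coefficient of variation, 5.2/6.2 = 0.84, would under a log-normal give √ln(1 + 0.84²) = 0.73 instead.

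**4. What it cannot do.** The stated 24 per group comes from n = 2(1.960 + 1.282)² × 5.2²/m² only if the bound 5.0 is entered as the margin m: n = 23, or 24 with the t distribution. With m = 1.2 it is 395 per arm, and with 1.24 (20% of 6.2, unrounded) it is 370. With 50 per arm and no true difference, power (noncentral t, 98 df, margin 1.2 / 1.24) is 20.7% / 21.8% without adjustment, 22.5% / 23.7% at R² = 0.1 and 36.5% / 38.6% at R² = 0.5. For 90% the residual SD would have to be 1.2/(3.242 × 0.2) = 1.85, that is R² = 1 − (1.85/5.2)² = 0.87. With 1.24 it would be 0.86.

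**The case against.** The strongest reply is that the protocol fixes very little here. The objective is one phrase in a list, any objective about hard stones needs a definition of hard, and a numeric HU field does not prevent a continuous analysis. That stands in part: the phrase is not a full analysis rule. Yet the threshold is the only form in which the protocol states the question, and the tests it gives as examples for secondary endpoints are simple comparisons that suit classes. Saying now that HU will be continuous is a real change to a stated choice.

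A reader might infer more: that the primary comparison is planned without adjustment, that neither density nor volume enters it, and that precision is therefore being lost. The document does not support this.

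- It names no primary model. The t-test and chi-square test are examples for secondary endpoints. Covariates may properly be set in a statistical analysis plan, which is not at hand.
- Volume does enter, as the denominator of J/mm³. Only its use as a covariate is unmentioned.
- Absence of stratification by density does not bias the comparison. Chance imbalance is already covered by the unadjusted standard error; adjustment narrows the interval.

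It is also true that the Table 1 cohorts are not this trial's population. By the titles in the reference list they include a ureteral-stone series and a percutaneous series. The median HU here is unknown.

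**Conclusion.** The point holds for the hard-stone objective and, for the primary comparison, as a recommendation rather than an error. The protocol ties hardness to a cut near the middle of the expected densities although the continuous value is collected. The loss is about 36% of the information if HU is roughly normal, the effect linear and the cut at the median. It is slightly more if the cut is off centre, and less if the effect is step-like.

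For the primary comparison, a named HU covariate would help if HU predicts J/mm³. The document gives no figure for that, so the 11 to 67% is conditional on an assumed R² of 0.1 to 0.4. No plausible R² brings 50 per arm near 90% power at the stated margin. The sample-size error is a separate and larger matter.

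**What to change.** 1. Answer the hard-stone objective with a model for ablation efficiency containing arm, continuous HU and their interaction. Report the arm difference over the observed HU range. Keep results at or below and above 1000 HU as a descriptive display.
2. Name continuous HU as a covariate in the primary non-inferiority comparison, and take the estimate and its interval from the arm term.
3. Keep model and margin on one scale. Section 6 sets the margin on the arithmetic mean (1.2 of 6.2 J/mm³), which suits an additive model. If a log-ratio model is chosen, restate the 20% as a ratio and give its direction: 1.20 and 1/0.8 = 1.25 are different readings.
4. Treat pre-operative volume as optional. It is measured before surgery and so is admissible, but it is tied to the endpoint's denominator and its measurement error would appear on both sides of the model. Use it only with a stated reason.

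Cost: no new data, visits or procedures. On the additive scale it is analysis wording only. A move to the log scale also changes the quantity estimated and requires the margin to be restated. Either should be settled before outcomes are seen.

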Perioperative fields will include total operative time, presence of preoperative alpha blockers, procedure time, laser time, setting of lithotripsy that was used most frequently during the case, total laser energy used, use of active fragment extraction (# of fragments beyond that for analysis/culture), 1st assist skill level (PGY level), use and size of ureteral access sheath, intra-operative complications, and treatment on any anticoagulation.

Postoperative fields will include length of hospitalization, postoperative complications, stone composition, need for ancillary procedures, stent duration, and stone-free status on postoperative low-dose CT imaging (axial slices 2.5mm and sagittal/coronal 3mm) using residual stone ABC grading (0 fragments, <2mm fragments, 2-4mm fragments) as recently recommended by Journal of Endourology. (Stern et al., 2023).

The trial will be a prospective, study of patients with renal stones 7-20 mm in size located at or above the level of the ureteropelvic junction. Total enrollment will be limited to 100 patients (50 ureteral and 50 renal) for the study with goal of 50 patients (25 ureteral and 25 renal) in each arm. This goal recruitment number is based on a power analysis for a noninferiority study utilizing a pre-determined non-inferiority margin of 20%, and was calculated to provide 90% power with a one-sided significance level of 0.025.

Table 1, adapted from (Solano et al., 2023), was constructed using results from recently published studies reporting ablation efficiency (J/mm³). The median ablation efficiency for TFL in the table was of 5.6 J/mm³ (Enikeev et al., 2021) with IQR 3-9.9. Assuming a normal distribution, the median and IQR values were used to estimate mean of 6.2 J/mm³ and standard deviation of 5.2 J/mm³. (Wan et al., 2014; Luo et al., 2018) Non-inferiority margin was set at 20% (6.2-1.2=5.0 J/mm³). Estimated mean difference between TFL and Tm:YAG ablation efficiencies was 0 based on a recent systematic review by an international expert in the field (Solano et al., 2023). Data was input into a validated sample size calculator <https://app.sampsize.org.uk/> as previously described. (Flight and Julious, 2016; Negida, 2020) A sample size of 24 participants per group (n=48 total) was found to provide 90% power to detect a non-inferiority margin of 20% with a one-sided significance level of 0.025.

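### The hypothesis claims similar clinical and safety outcomes, but the only analyses named for them are tests of difference, which cannot support that claim at 50 per arm

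*Protocol*

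**What the plan says.** Protocol section 4 (Specific Aims/Hypotheses) puts two claims in one hypothesis: non-inferiority on dusting ablation efficiency and speed, "with similar clinical and safety/complication outcomes". The same section lists stone-related clinical outcomes "and safety/complication profile of both laser systems" among the secondary objectives.

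Section 6 (Research Design and Methods) then divides the analysis:

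- For the primary endpoints: "Non-inferiority analysis will be conducted for the primary endpoints, with a pre-specified non-inferiority margin of 20"%.
- For the rest: "Secondary endpoints will be compared using appropriate statistical tests (e.g., t-test, chi-square test").

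The clinical and safety data are described in section 6: "Postoperative fields will include length of hospitalization, postoperative complications, stone composition, need for ancillary procedures, stent duration", together with graded stone-free status on CT. The target is 100 patients, "with goal of 50 patients (25 ureteral and 25 renal) in each arm". Section 8 (Recruitment) adds that "participants will be randomized in a 1:1 ratio".

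The protocol gives no margin, equivalence bound, interval criterion, expected rate or power for any clinical or safety outcome. The recruitment goal, "calculated to provide 90% power with a one-sided significance level of 0.025", is derived from ablation efficiency and from in-vitro ablated weight only.

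**The concern.** A t-test or chi-square test can give evidence against equality. It cannot give evidence for it. For the ablation endpoint the protocol recognises this and attaches a margin to the no-worse claim. The companion claim in the same sentence, about clinical and safety outcomes, has no such device, and the tests named for it answer a different question.

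With those tests, the only result that could be taken as favouring similarity is a non-significant one. In a trial of this size that result is likely over a range of real differences. Section 5 (Background and Significance) states that no prospective comparative trial has been published, so readers may rely on what this trial says about safety.

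**Working it through.** **Inputs.** From the protocol: 50 per arm, allocation 1:1. Assumed, because the protocol gives none: event rates, and a two-sided 5% level for the chi-square test. There is no stated power for clinical or safety outcomes to reproduce. The protocol's sample-size figures concern ablation endpoints and are not used here.

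**1. Power of the test of difference.** With pbar the mean of p1 and p2, the normal approximation is

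power ≈ Φ{ [ |p1−p2|·√n − 1.96·√(2·pbar(1−pbar)) ] / √(p1(1−p1) + p2(1−p2)) }

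For 10% versus 20%, n = 50, pbar = 0.15:

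- |p1−p2|·√n = 0.10 × 7.071 = 0.707
- 1.96 × √0.255 = 0.990
- √(0.09 + 0.16) = 0.500
- power ≈ Φ((0.707 − 0.990)/0.500) = Φ(−0.565) ≈ 0.286

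The exact column sums the joint probability of all pairs of binomial counts for which the Pearson chi-square test is significant.

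| Assumed rates | Normal approximation | Exact | Non-significant (1 − exact) |
|---|---|---|---|
| 5% vs 10% | 15.5% | 14.5% | 85.5% |
| 10% vs 20% | 28.6% | 30.3% | 69.7% |
| 15% vs 30% | 43.4% | 44.3% | 55.7% |
| 20% vs 40% | 59.0% | 59.5% | 40.5% |
| Stone-free 80% vs 70% | 20.9% | 21.2% | 78.8% |

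The last row treats stone-free status as yes/no, whereas the protocol grades it. For 80% power, 5% versus 10% would need 435 per arm and 10% versus 20% would need 199. For a continuous outcome, power at 50 per arm is 32% for a difference of 0.3 SD and 71% for 0.5 SD.

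**2. What an interval would show.** With the same rate p in each arm, the 95% half-width is 1.96 × √(2p(1−p)/50).

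- p = 5%: 1.96 × √0.0019 = 8.5 points
- p = 10%: 1.96 × √0.0036 = 11.8 points
- p = 20%: 1.96 × √0.0064 = 15.7 points

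So even identical observed rates of 10% would leave a 10-point excess inside the interval.

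**3. One possible result.** Suppose 5/50 versus 10/50.

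- Test: z = 0.10/√(0.15 × 0.85 × 2/50) = 0.10/0.0714 = 1.40, so p ≈ 0.16.
- Interval: 0.10 ± 1.96 × √((0.09 + 0.16)/50) = 0.10 ± 0.139, or −3.9 to +23.9 points.

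The test is non-significant, yet the interval is compatible with a large excess.

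**4. Could similarity be tied to a bound at this size?** Take, for illustration, a 10-point margin, equal true rates and one-sided 0.025. Power at 50 per arm is Φ(0.10/√(2p(1−p)/50) − 1.96). The number needed for 80% power is (1.96 + 0.84)² × 2p(1−p)/0.10².

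| True rate in both arms | Power at 50 per arm | Per arm for 80% power |
|---|---|---|
| 5% | 63% | 75 |
| 10% | 39% | 142 |
| 15% | 29% | 201 |
| 20% | 24% | 252 |

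**The case against.** A reader might infer that the protocol prescribes reporting a non-significant safety comparison as similar safety. It does not. No section states a decision or reporting rule for these outcomes. The tests are given as examples of appropriate ones, so intervals or a margin are not ruled out, and a statistical analysis plan that is not shown could add them. The absence of interval detail from a protocol is therefore not in itself a fault.

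A reader might also infer that a doubling of complications would usually be missed. That depends on rates the protocol does not give. At 20% versus 40% the test is significant in about 60% of trials. Nor would the data be hidden: section 6 also plans to summarise categorical post-operative data as counts and percentages, so a doubling would be visible if these are shown by arm, which is the natural reading.

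Nor do the documents support treating safety as half of the trial's conclusion. Section 4 places it last among the secondary objectives, in language that can be read as descriptive, and section 5 restates the aim without it.

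All of this stands, and it limits the weight of the point. It does not remove the mismatch. The word *similar* is in the protocol's own hypothesis, both tests named are tests of difference, and the non-inferiority analysis is assigned to the primary endpoints.

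**Conclusion.** The point holds as a mismatch between hypothesis and analysis. The protocol hypothesises similar clinical and safety outcomes, and the analyses it names for them cannot support that. No rule equating non-significance with similarity is stated, but the named tests offer no other route to the hypothesised conclusion.

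For the doublings examined, a true difference would go undetected in about 40% to 85% of trials, depending on the base rate. These figures rest on assumed rates, a two-sided 5% chi-square test and a full 50 per arm. Fewer analysed patients would lower the power further.

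The point is minor to moderate. It concerns secondary endpoints and leaves the primary comparison untouched.

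**What to change.** - In section 6, state that each clinical and safety outcome will be reported as a between-arm difference with a 95% confidence interval. P-values may stay alongside.
- In section 4, remove *similar* from the hypothesis, or say that the clinical and safety outcomes are descriptive.
- Limit the conclusion on these outcomes to the differences that the interval excludes.

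This changes wording and a small part of the reporting. It needs no extra patients or procedures. The price is a weaker safety claim: with 10% events per arm the trial could say only that differences beyond about 12 points are excluded.

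Keeping *similar* and tying it to a pre-stated bound is possible but is a real trade-off. At 50 per arm, the illustrative 10-point margin would be met in only 24% to 63% of trials with truly equal rates, so that choice risks a failed claim or calls for a larger trial.
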